We will include 20-25 women with $\text{BMI} > 25 \text{ kg/m}^2$ who are exclusively breastfeeding a singleton term infant. Participants will provide a written informed consent. The assessments will be completed between 5 and 12 weeks postpartum, with the first assessment 5-9 weeks postpartum. No formal power calculation is possible for the acute study due to the exploratory nature of the research. We will continue including participants until we have complete data for all three sets of conditions for at least 20 participants. The crossover design of this study will decrease the interindividual variation in the statistical analysis. The women will serve as their own controls, which will remove any interindividual biological variance in breastmilk.

Experimental design

This will be a randomised cross-over study, in which all participants undergo three different conditions, in random order (Fig. 2):

- 1) Moderate intensity exercise; 48 min at $\sim 70\%$ of heart rate maximum
- 2) High-intensity exercise; 4 x 4 min at 90-95% of heart rate maximum
- 3) No exercise. Resting in the lab.

[figure not shown]

Fig. 2. Exercise will take place at 1000h, and breastmilk will be sampled at 0 h (immediately after exercise), + 1 h and + 4 h after exercise/no exercise. Dietary intake will be standardised on the day before and on the day of the experiment. Moderate intensity exercise (A), High intensity exercise (B) and No exercise (C) will be separated by one week and will be undertaken in random order.

Participants will walk or run on a treadmill during both exercise conditions. *Inclusion criteria:* Besteen 5+6 and 8+6 weeks postpartum at the first condition in the study, exclusively breastfeeding a term infant. *Exclusion criteria:* Known cardiovascular disease, type 1 or 2 diabetes.

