Acute Effects of Endurance Exercise with Moderate and High Intensity on Breast Milk Composition Among Women with Overweight/Obesity

Acronym: YT

NCT number: NCT05745922

Document date: 07. September 2025

Statistical Analysis Plan

Study design: Randomized crossover study

Aim: Determine the effect of moderate-intensity continuous training and high-intensity interval training on human milk concentrations of metabolites, lipids, cytokines, hormones and miRNAs in lactating women with overweight/obesity.

Overview:

- Up to N=30 women with $\text{BMI} > 25 \text{ kg/m}^2$
- Each participant goes through three conditions in random order (six possible sequences) and has milk sampled at four time points per condition (one pre-condition and three post-condition).
- Washout period: 1 week between conditions
- The samples are analysed for a range of outcome variables within different molecular data ('omics') categories.

Conditions:

- C1: No exercise, resting in the lab
C2: Moderate-intensity continuous training
C3: High-intensity interval training

Time points:

- T1: 7 am (pre-condition)
T2: 11 am (immediately after condition)
T3: 12 am (1-hour post-condition)
T4: 15 am (4 hours post-condition)

Pre-planned outcome groups measured in human milk:

- Targeted NMR metabolomics (GCF)
Metabolomics + lipidomics profile panels (Metabolon)
Cytokines (Olink)
Hormones (insulin, ghrelin, leptin, adiponectin, IGF-1)
miRNA (GCF)

Statistical analysis plan

For each outcome category, the primary objective is to evaluate the effect of conditions C2 and C3 on the outcome variables at time points T2, T3, and T4, using condition C1 and time point T1 as references. Outcomes measured in all participants will be analysed according to the intention-to-treat principle, whereas outcomes measured only in participants who followed the protocol perfectly will be analysed according to the per-protocol principle. The decision whether to include all samples or only those from participants who complied with the protocol will depend on the costs of including the extra (non-compliant) samples for each outcome group.

We will perform the following six analysis steps for all outcome groups:

1) Data preparation (batch adjustment, log transformation, imputation)

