- If needed, the outcome data will be batch adjusted, imputed (e.g. using the R package *zCompositions*), and log transformed appropriately before analysis. Adjustments and transformations will depend on whether the data is already normally distributed, and if it is required for the method in question.
- The metabolomics data from Metabolon already comes in a log-transformed, batch-normalized version where missing values (below the detection limit) are imputed to the observed minimum for that metabolite after batch normalization. These will be used in all analyses.

2) Principal component analysis (PCA)

- We will use PCA to detect outliers and identify global structures/important features by capturing the maximum variance in the dataset, and test if the data separates according to the conditions in an unsupervised setting.
- We will identify the number of PCs that explain 95% of the variation in the data at baseline, for use in multiple testing adjustment.

3) Linear mixed model (LMM) analyses:

- We will use LMM analyses to evaluate the effects of each condition and time point on all outcome variables:
- We will analyse the effects of time and time-condition interaction as fixed effects, and participant ID as a random intercept (Eq 1). The analysis will be reference coded, with C1 (no exercise) and T1 (morning) as reference points. We will not adjust for or subtract baseline values in the model.

Eq. 1: $\text{value} \sim \text{time} + \text{time:condition} + (1|\text{id})$

- We will run the LMM analyses using e.g. the lme4 R package, and estimate p-values using the Satterthwaite method, e.g., as implemented in the lmerTests R package.
- Multiple testing correction: We will use a multiple testing corrected p-value threshold determined by dividing the alpha level (0.05) by the number of PCs explaining 95% of the variation in the outcome data at baseline.
- For variables passing the multiple testing corrected p-value cut-off, we will test for potential carry-over effects by adjusting for sequence (Eq. 2) in sensitivity analysis:

Eq. 2: response matrix ~ time + time:condition + sequence + sequence:condition + time:sequencec:condition + (1|id)

4) Repeated Measures (RM)-ASCA+

- We will use RM-ASCA+ to evaluate the overall effect of each condition and time point on each outcome data category. We will model all variables within the same data category together in a multiple-response variable analysis.

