- We will analyse both the combined and separate effects of time and time-condition interaction as fixed effects, and participant ID as a random intercept (Eq 3). The analysis will be reference coded, with C1 (No exercise) and T1 (morning) as reference points. We will not adjust for or subtract baseline values in the model.

Eq. 3: response matrix ~ time + time:condition + (1|id)

- Each variable will be scaled by the standard deviation of the baseline (morning) samples across conditions.
- We will use cluster bootstrapping with 1000 iterations to validate the findings and generate confidence intervals.

The results from the LMM and RM-ASCA+ analyses will guide follow-up analyses using additional machine learning models (PLS-DA, t-SNE).

5) Partial Least Squares Discriminant Analysis (PLS-DA)

- Supervised machine learning approach to analyse differences between the conditions. We will provide the model with a response matrix specifying the conditions, and the model will maximize separation between the conditions. The

method works well with small datasets and multiclass scenarios (here: multiple conditions).

- We will use PLS-DA for feature selection/to explore global structures in the data or find variables that are especially important for one time/condition compared to another. The LMM and RM-ASCA+ analyses will guide the selection of conditions/time points for comparison.
- We will perform cross-validation and permutation testing with 1000 repetitions.

6) T-Distributed Stochastic Neighbour Embedding (t-SNE)

- We will use t-SNE in an exploratory analysis to look for clusters of variables by preserving local relationships (pairwise similarities between data points, clusters).

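### Non-detects set to the observed minimum shrink condition effects in the LMM, and separately leave the morning-SD scaling in RM-ASCA+ unstable or undefined for rarely detected metabolites

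*SAP*

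**What the plan says.** SAP step 1 (Data preparation) states that the Metabolon metabolomics data arrive log-transformed and batch-normalised, and that "missing values (below the detection limit) are imputed to the observed minimum for that metabolite after batch normalization". It adds: "These will be used in all analyses". That covers PCA, the Eq. 1 LMM, RM-ASCA+, PLS-DA and t-SNE.

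Step 4 (RM-ASCA+) adds a scaling rule: "Each variable will be scaled by the standard deviation of the baseline (morning) samples across conditions". This rule appears under step 4 only; step 3 (LMM) does not scale.

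Neither document gives a minimum detection rate, a model for censored values, a detected/not-detected analysis, a sensitivity analysis for the imputation, or a rule for a morning SD at or near zero. For data other than the Metabolon metabolomics, step 1 leaves batch adjustment, imputation and transformation to be decided as needed.

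**The concern.** A value below the detection limit is known only to lie below it. Giving all such values one number and analysing them as measured pulls cell means together, so a real difference between exercise and rest is under-estimated. The more values are censored, the larger the loss.

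The scaling in step 4 raises a second, separate problem. If a metabolite is mostly undetected in the morning, most of its morning values are the same number and their SD is small. Dividing by that SD lets a few detected values decide the size of the scaled effect. If every morning value sits at the floor, the SD is zero and the scaled variable does not exist. RM-ASCA+ models all variables of a category together, so a few unstable ones can affect the shared components. The LMM and RM-ASCA+ results then jointly guide which conditions and time points go to PLS-DA.

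**Working it through.** The plan states no power, effect or detection figure, so there is nothing of its own to reproduce.

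**Inputs from the documents**
- N: at least 20 completers (Protocol, Participants, which asks for "complete data for all three sets of conditions for at least 20 participants") and up to 30 (SAP, Overview). One morning sample in each of 3 conditions gives 60 to 90 morning values.
- Model: Eq. 1. With complete balanced data, the C3−C1 contrast at T2 is a difference of two cell means.
- Threshold: "dividing the alpha level (0.05) by the number of PCs explaining 95% of the variation in the outcome data at baseline". The number of PCs is not given; 20 is assumed for illustration, so 0.05/20 = 0.0025.

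**Assumed, not in the documents:** normal values on the log scale; detection rates; two settings. Setting A has total SD 1, intraclass correlation 0.5 and an effect of ±0.5 SD. Setting B has between-woman SD 1.0 and within-woman SD 0.7, so total SD √(1.00 + 0.49) = 1.22, and an effect of ±0.5, which is 0.5/1.22 = 0.41 SD.

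**Step 1: LMM shrinkage.** For latent mean μ, SD 1 and floor c, the expected floored value is

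E(μ) = cΦ(c−μ) + μ[1−Φ(c−μ)] + φ(c−μ).

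With 50% censored in the reference cell, c = 0 and E(0) = 0.3989.
- Increase: E(0.5) = 0.5×0.6915 + 0.3521 = 0.6978. The difference is 0.2989, and 0.2989/0.5 = 0.60 is kept.
- Decrease: E(−0.5) = −0.5×0.3085 + 0.3521 = 0.1978. The difference is −0.2011, and 0.40 is kept.

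The same formula at other censoring shares (no time-of-day shift), with the SD of the floored values:

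| Censored | A: increase kept | A: decrease kept | B: increase kept | B: decrease kept | Floored SD (latent 1) |
|---|---|---|---|---|---|
| 20% | 0.86 | 0.72 | 0.85 | 0.74 | 0.83 |
| 50% | 0.60 | 0.40 | 0.58 | 0.42 | 0.58 |
| 80% | 0.28 | 0.14 | 0.26 | 0.15 | 0.31 |
| 95% | 0.08 | 0.03 | 0.08 | 0.03 | 0.12 |

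Simulation of the design, with the observed minimum as the floor, agrees: about 85%, 58% and 26% of a +0.5 effect, and about 72%, 42% and 15% of a decrease.

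**Step 2: what this does to the tests (simulation).** Flooring also shrinks the residual variance, so power falls less than the estimate does.
- Setting B, N = 25, p < 0.05: power 0.71 fully observed, 0.69 at 20% censored, 0.61 at 50%, 0.41 at 80%, 0.25 at 95%.
- Setting A, N = 20, p < 0.05: about 0.60 fully observed, 0.52 at 50% censored, 0.33 at 80%, 0.24 at 90%. At p < 0.0025: about 0.20 fully observed, 0.04 at 90%.
- Type I error at 0.05 stays at about 0.04 to 0.06 down to 10% detection.

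**Step 3: RM-ASCA+ scaling.** Scaled effect = floored difference / floored morning SD (setting A).
- +0.5 SD, no time-of-day shift: 0.2989/0.58 = 0.51 at 50% censored. The floor and the smaller SD nearly cancel.
- −0.5 SD, no shift: −0.2011/0.58 = −0.34 at 50% censored and (−0.5×0.14)/0.31 = −0.23 at 80%, so attenuated.
- +1 SD, no shift, 90% censored, N = 20 (simulation): median about 1.3, 5th to 95th percentile 0.4 to 4.7.
- Later samples 1 SD above morning, 90% of morning values censored, N = 20 (simulation): +0.5 SD becomes about 1.5, and +1 SD becomes about 3.6 (1.5 to 12).

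**Step 4: morning SD exactly zero.** If samples were independent with morning detection rate d, P = (1−d)^(3N).
- d = 5%: 0.95^60 = 0.046 for 20 women; 0.95^90 = 0.010 for 30. Correlation within a woman raises this to about 8–13% and 2–4% in simulation.
- d = 1%: 0.99^60 = 0.55; 0.99^90 = 0.40.

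**Step 5: does a censored model help?** For a true +0.5 SD at N = 20, floored values against a left-censored (Tobit) fit gave 0.44 against 0.51 at 80% detection, 0.29 against 0.49 at 50%, and 0.18 against 0.46 at 30%.

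**The case against.** The best defence is that the study is exploratory and the LMM screens on p-values, which suffer much less than the estimates. At 50% censoring in setting B the estimate falls to 58% of the truth, but power falls only from 0.71 to 0.61, with no excess of false positives. This stands and limits the LMM part to biased effect sizes, plus lost power where censoring is heavy.

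Several stronger readings are tempting, and the documents do not support them:
- That the morning-SD scaling causes the LMM shrinkage. Scaling is stated for RM-ASCA+ only; the LMM shrinkage comes from the imputation alone.
- That the plan would miss a metabolite appearing only after exercise. In a simulation with detection only at C3/T2, in 20% of women (half-normal log values above the limit assumed), Eq. 1 had power 0.93 at N = 20 and 0.99 at N = 30 at p < 0.05, and 0.70 and 0.92 at p < 0.0025. For such a metabolite it is the RM-ASCA+ scaling that fails, because its morning SD is zero.
- That RM-ASCA+ effects are always inflated. Small increases roughly cancel. Without a time-of-day shift decreases are attenuated; inflation needs a large increase or a rise after the morning.
- That the bootstrap will divide by zero. The SAP does not say whether scaling is recomputed in each resample.
- That all outcome groups are affected. The rule quoted is for the Metabolon metabolomics data.

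It is also fair to say that no detection rates are given, so the problem could touch few variables. But the Protocol expects more than 1000 metabolites from this platform, and a rule for sparse ones is best fixed before the results are seen.

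**Conclusion.** The point holds, in two separate parts. First, the floor shrinks LMM condition effects: about 85%, 58% and 26% of a +0.5 effect is kept at 20%, 50% and 80% censoring, and about 72%, 42% and 15% of a decrease. Type I error is near nominal, and power loss is modest except under heavy censoring. Second, RM-ASCA+ has no protection against a morning SD at or near zero. At 5% morning detection the floored SD is about 0.12 of its true value, and it is exactly zero for roughly 2–13% of such metabolites, depending on N and the within-woman correlation.

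These sizes rest on normal log values, the assumed variances and the assumed detection rates. How many metabolites are affected cannot be worked out from the documents. The change is worth making because it is cheap and can be fixed in advance; the point does not show that the LMM screen is invalid.

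**What to change.** Amend SAP steps 1, 3 and 4 before condition labels are attached to the data:

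1. **RM-ASCA+ entry.** Set a minimum morning detection rate (for example 50%; the sponsor chooses), and exclude any variable with a morning SD at or near zero from morning-SD scaling. The rate should be the morning one. A metabolite detected in 40% of morning and 90% of later samples has (40 + 3×90)/4 = 77.5% detection overall, so an overall limit could let it through.
2. **LMM.** Keep Eq. 1 for every variable with non-zero variance. An overall cut-off would lose a metabolite seen only at C3/T2, whose detection cannot exceed 1/12, about 8%. Where censoring is material (for example above 20%), add as a sensitivity analysis a left-censored (Tobit) mixed model if the reference cells contain detected values. If they do not, its maximum-likelihood contrast is not finite, so compare detected/not detected by condition and time instead.
3. **Reporting.** Give the detection rate with each result.

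Cost: SAP wording and some extra analysis, with no new samples. The downside is that sparsely detected metabolites leave the RM-ASCA+ model and are reported separately. Using the same rule for the cytokine panel is optional and does not follow from the text quoted.

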Breastmilk samples (~ 25 mL) will be collected at 4 timepoints in each condition. Samples obtained after exercise and in the control condition (no exercise) will be compared to a 'baseline' sample obtained at the first breastfeeding in the morning (06-0700 h) on the same day (Fig 2). Prior to the experimental protocol, all participants will undergo a maximal effort exercise test to establish their cardiorespiratory fitness (maximum oxygen uptake) and heart rate maximum. This test will be undertaken at a separate day, at least two days prior to the first experimental condition, and takes about 30 minutes. On the same day, we will also estimate the participants' body composition using a bioimpedance scale (InBody 720), and infant weight and length. We will estimate infant body composition using biompedance (BioScan tough i8-nano).

Standardised meals

Participants will be asked to register their last meal the day before the first day of experiment, as well as the breakfast and lunch on the first day of experiment using a food diary. They will be asked to repeat the exact same meals at standardised time-points in the two following days of experiment (Fig. 2).

Questionnaires

Participants will complete the International Physical Activity Questionnaire (IPAQ) at baseline. They will also provide information on their age, ethnicity, date of delivery, the infant's birth weight, length and head circumference, and whether they are smoking or taking medications.

Breastmilk sampling

Breastmilk will be sampled by the women themselves, using an electric breast pump provided to them (Medela Symphony, Switzerland). Participants will be given a detailed instruction sheet and a link to a video for milk collection procedures. Breastmilk will be collected at the described time-points in the experimental protocol. For each mother, breastmilk will be collected from one breast (of her own

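### Eq. 1 has no visit-day random effect, so if milk composition varies from day to day its p-values are too small for condition contrasts and too large for changes from T1

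*SAP*

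**What the plan says.** The SAP Overview says each participant "has milk sampled at four time points per condition (one pre-condition and three post-condition". The Protocol's Fig. 2 caption (Experimental design) says the three conditions "will be separated by one week and will be undertaken in random order". Condition is therefore assigned to a whole day.

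Step 3 of the SAP gives the model for each outcome variable: "We will analyse the effects of time and time-condition interaction as fixed effects, and participant ID as a random intercept (Eq 1". It continues: "The analysis will be reference coded, with C1 (no exercise) and T1 (morning) as reference points", and "We will not adjust for or subtract baseline values in the model". P-values use Satterthwaite degrees of freedom, and the threshold is 0.05 divided by the number of principal components that explain 95% of baseline variation.

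Eq. 2 adds fixed sequence terms but ends with the same random part, "sequence:condition + time:sequencec:condition + (1|id". It is run only for variables that have already passed. Eq. 3, for RM-ASCA+, is "response matrix ~ time + time:condition + (1|id".

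The Protocol (Experimental design) describes a within-day comparison: samples "will be compared to a 'baseline' sample obtained at the first breastfeeding in the morning (06-0700 h) on the same day".

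**The concern.** With a participant intercept alone, the model has one correlation for any two samples from the same woman, whether they are taken an hour or a week apart. If anything shifts all of one day's samples together, that assumption fails. A condition contrast at one time point compares two different days and carries the visit variance in full. A change from T1 compares samples within a day, and the visit effect cancels. Eq. 1 charges both the same intermediate amount.

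The step 3 p-values decide which variables pass the corrected threshold, and the mixed-model results help choose the PLS-DA comparisons. Condition contrasts would pass too often. Time coefficients, and differences in change from T1 if these are tested, would pass too rarely.

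**Working it through.** The plan states no variance, power or error figure, so there is none to reproduce.

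**Inputs.** Three visit days per woman and four samples per day (Protocol, Experimental design; SAP, Overview). n = 20 is the minimum number of women with complete data (Protocol, Participants), and 30 is the maximum (SAP, Overview). Assumed: the ratio r = s_v²/s_e² of visit variance to within-day residual variance, which the documents do not give; normal, complete data; a visit effect that is constant within the day; two-sided tests.

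**Residual under Eq. 1.** There are 12n observations. Removing n participant means and 11 further fixed effects (3 time, 8 time-by-condition) leaves 11(n−1) df, or 209 at n = 20. Of these, 2(n−1) are between visits, with expected mean square s_e² + 4s_v², and 9(n−1) are within visits, with expected mean square s_e². Pooled:

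[2(s_e² + 4s_v²) + 9s_e²]/11 = s_e² + (8/11)s_v²

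**What each comparison needs.**

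- C2 or C3 versus C1 at one time point: true variance 2(s_e² + s_v²)/n. Ratio of Eq. 1 SE to true SE: √[(1 + 8r/11)/(1 + r)]. At r = 1 this is √(1.727/2) = 0.93. The limit for large r is √(8/11) = 0.85.
- Change from the same-day T1 sample: true variance 2s_e²/n. SE ratio: √(1 + 8r/11). At r = 1 this is √1.727 = 1.31. A difference in change has true variance 4s_e²/n and the same ratio.

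**Type I error under Eq. 1** (n = 20, 100,000 simulated null data sets per r, T2 to T4 averaged for the condition contrast):

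| r | SE ratio, condition contrast | Error at 5% | Multiple of nominal at 0.05/10 | Multiple at 0.05/30 | SE ratio, change from T1 | Error at 5% |
|---|---|---|---|---|---|---|
| 0.1 | 0.99 | 5.3% | 1.1 | 1.1 | 1.04 | 4.3% |
| 0.25 | 0.97 | 5.7% | 1.3 | 1.3 | 1.09 | 3.3% |
| 0.5 | 0.95 | 6.2% | 1.5 | 1.7 | 1.17 | 2.3% |
| 1 | 0.93 | 6.9% | 1.9 | 2.2 | 1.31 | 1.1% |
| 2 | 0.90 | 7.8% | 2.4 | 2.9 | 1.57 | 0.3% |

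The divisors 10 and 30 are illustrative, because the SAP cannot yet state the number of components. At r = 0 the simulated error is 4.9%, as it should be. At n = 30 the condition-contrast error is again 5.3% to 7.8%, so recruiting more women does not help.

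**Lost power.** At r = 1, a difference in change from T1 that has 80% power under the correct model has about 59% under Eq. 1.

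**With a visit intercept.** The condition contrast is then judged against MS_v/4 + 3MS_e/4, where MS_v and MS_e are the between-visit and within-visit mean squares, with Satterthwaite df. Its error at nominal 5% returns to 5.0%.

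**Fitted example.** In one simulated data set (n = 20, r = 1), a REML fit of Eq. 1 gave SE 0.386 for every time and time-by-condition coefficient. Adding the visit intercept gave 0.322 for time and 0.407 for time-by-condition.

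**The case against.** The algebra is not in dispute; the weight is. Visit variance is unobserved, and the design works to keep it small: repeated meals, fixed sampling times, one breast throughout. For r up to 0.5 the condition-contrast error is at most 6.2%. The multiples at strict thresholds depend on an unknown component count. Sixty baseline samples allow at most 59 components, which would explain all the variation rather than 95%. The five hormones allow at most five, so the threshold there is at least 0.01 and the inflation is 1.1 to 2.1 times. The Protocol calls the research exploratory.

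Much of this stands as a limit on size. The inflation of a single coefficient is modest, and false rejection at T2, T3 and T4 together is rare with or without the visit term (at most 1.5% against 0.8%). It does not show that visit variance is zero. Visits fall between 5 and 12 weeks postpartum with no period term in Eq. 1. The Protocol (Cytokine and hormone profiling) describes subclinical mastitis as common and disruptive to inflammatory components. It plans to adjust for mastitis, but Eq. 1 has no such term.

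Two further points stand. The SAP's reference to both C1 and T1 could mean a difference in change from T1, in which case only the conservative error applies. And the visit term restores calibration only under the assumptions above. With r = 1 and assumed residual SDs of 0.7, 1, 1 and 1.4 at T1 to T4, error at T4 was 12.2% under Eq. 1 and still 9.7% with the visit term.

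The RM-ASCA+ cluster bootstrap does not answer the concern. It does not produce the step 3 p-values, and the SAP does not say what the cluster is.

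**Conclusion.** The concern holds, conditionally. Eq. 1 is calibrated for both kinds of comparison only if visit variance is zero, and nothing in the documents shows that it is. Otherwise the condition contrasts at a single time point are moderately anti-conservative, more so in relative terms at the corrected threshold, and changes from T1 are conservative, severely so when visit variance is large. The algebra is certain for complete, balanced data; the size in this trial is not known. This should be fixed before analysis, but it does not undermine the design.

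**What to change.** In Eq. 1 and Eq. 2, replace the random part with `(1|id) + (1|id:condition)` and keep Satterthwaite degrees of freedom. Each woman has one visit per condition, so `id:condition` identifies the visit day. Use the same structure in Eq. 3 for consistency. State in the same paragraph whether the tested contrast is the difference from C1 at each time point or the difference in change from T1.

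The cost is one term in the SAP and the code, with no new data. Some variables will give a singular fit with zero visit variance: at n = 20, about 52% of fits when the true visit variance is zero and 11% at r = 0.1. Those fits reduce to the current model, and the SAP should say that this is expected and acceptable.

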choice) for the entire study. The collected single full breast milk samples will be mixed and aliquoted into 10 x 1.8 mL sterile cryotubes and 1 x ~20 mL sterile vial, with the remaining milk for the mother to use. Samples will be frozen immediately after collection. Samples obtained after exercise training will be immediately transferred (on ice) to -80°C. The remaining samples (morning samples) will be frozen by the participants themselves at -20°C for up to 4 days before it will be transferred (cold chain) to the laboratory where it will be frozen at -80°C until analysis. The 10 x 1.8 mL aliquots will be used in the planned analyses, described below, whereas the additional 20 mL sample will be stored in a biobank for future analyses when additional funding and/or collaborations become available.

Breastmilk composition

Targeted NMR Metabolomics

Metabolic profiling of breastmilk will be analysed using nuclear magnetic resonance (NMR) spectroscopy using a Bruker Avance III Ultrashielded Plus 600 MHz spectrometer (Bruker Biospin GmbH, Germany) at NTNU MR Core Facility. After removal of residual lipids and proteins as previously described⁵⁴, each filtered sample (350 µL) will be mixed with 350 µL of 0.1 M phosphate buffer solution (pH 7.4) containing sodium 3-trimethylsilyl-(2,2,3,3-2-H3)-1-propionate (TSP) (final concentration 2 mM), and then 650 µL will be transferred into a 5 mm wide NMR tube. Metabolites will be assigned using Bruker AMIX software v.2.5 and Chenomx v.7.11 (Chenomx Inc., Canada), matching spectra to reference databases of metabolites. A mother's secretor status reflects her blood group antigens and determines her ability to synthesise certain HMOs, thus the secretor status for each individual will be determined by the high abundance (secretor) or near absence (non-secretor) of the HMO 2'-fucosyllactose in the respective milk samples with a cutoff of 100 nmol 2'FL/mL, as previously described.⁵⁵ Secretor status will be accounted for in the analysis by doing sub-group analyses of secretors vs. non-secretors.

Untargeted Global Metabolomics and Complex Lipid Panel Analysis

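### Eq. 1 gives the same-day morning sample no weight in the exercise contrasts, so adjusting for it could gain precision at small cost

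*SAP*

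**What the plan says.** The protocol (Experimental design) says that samples from the exercise and resting conditions are "compared to a 'baseline' sample obtained at the first breastfeeding in the morning (06-0700 h) on the same day". The SAP's primary objective is the effect of C2 and C3 at T2, T3 and T4, "using condition C1 and time point T1 as references".

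Step 3 then fits Eq. 1, value ~ time + time:condition + (1|id). On coding it says: "The analysis will be reference coded, with C1 (no exercise) and T1 (morning) as reference points". It adds: "We will not adjust for or subtract baseline values in the model". Step 4 repeats that rule for RM-ASCA+, and Eq. 3 has the same structure. No reason is given for leaving T1 out of the contrasts, and the SAP does not list the contrasts that will be reported.

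**The concern.** T1 makes up 3 of each woman's 12 samples. It is the only measurement on each experimental day that precedes the condition. If a woman's morning value on a given day predicts her later values that day, chance day-to-day differences in T1 explain part of the noise in C2 minus C1 and C3 minus C1. A model that ignores T1 leaves that noise in.

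This matters more than usual here. The protocol recruits "until we have complete data for all three sets of conditions for at least 20 participants" and has no power calculation. Each LMM p-value faces a multiplicity-corrected threshold, and the LMM results help to guide the later PLS-DA and t-SNE analyses.

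**Working it through.** **Inputs.** From the documents: three conditions and four time points; n = 20 (protocol minimum with complete data) and n = 30 (SAP: "Up to N=30 women"); T1 at 7 am and T2 at 11 am, with T3 and T4 read as noon and 15:00, so gaps of 4, 5 and 8 hours from T1. Assumed: rho from 0 to 0.7. The documents give no variance or correlation, so there is no stated figure to reproduce.

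**Step 1: the weight of T1 under Eq. 1.** Time has 4 parameters including the intercept, and time:condition adds 4 × 2 = 8. That makes 12 parameters for 12 cells. With complete data the fitted cell means are the raw cell means, so

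coefficient(Tk:C2) = mean(C2, Tk) − mean(C1, Tk).

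T1 does not appear. Exact generalised least squares weights confirm this: +1, −1, and 0 on every T1 sample. They stay the same if T1 means are held equal across conditions while (1|id) is the only random effect. In a simulated data set the T4:C2 coefficient was 0.1907. The raw difference at T4 was also 0.1907, while the difference in change was 0.2028. Adding large noise to every T1 value left the coefficient at 0.1907. With about 10% of samples missing at random, single T1 samples regain a small weight, up to about 0.10 of a full observation.

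**Step 2: what adjustment would gain.** Let s² be the within-woman variance at one time point.

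- Plain difference (Eq. 1): 2s²/n.
- Subtracting T1: 4s²(1 − rho)/n, a multiplier of 2(1 − rho).
- Adjusting for the same-day deviation of T1 from the woman's mean: (2s²/n)(1 − rho²)[1 + 1/(2(n − 1) − 2)]. The bracket is the cost of estimating the slope: 1 + 1/36 at n = 20 and 1 + 1/56 at n = 30.

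Variance multipliers against Eq. 1, same rho at T2 to T4, n = 20:

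| rho | adjusted | approximate SE change | subtracted |
|---|---|---|---|
| 0 | 1.028 | +1% | 2.0 |
| 0.2 | 0.987 | −1% | 1.6 |
| 0.3 | 0.935 | −3% | 1.4 |
| 0.5 | 0.771 | −12% | 1.0 |
| 0.7 | 0.524 | −28% | 0.6 |

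For example, at rho 0.5: 0.75 × 37/36 = 0.771. At n = 30 it is 0.75 × 57/56 = 0.763. Simulation agrees to about 0.01.

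**Step 3: if the correlation decays with time.** Assume correlation = r^(gap/4), where r is the T1–T2 value. At r = 0.5 this gives 0.50, 0.5^1.25 = 0.42 and 0.5² = 0.25 at T2, T3 and T4. The formula gives multipliers of 0.77, 0.85 and 0.96; simulation gives 0.78, 0.86 and 0.96. Simulated values are 0.93, 0.98 and 1.02 at r = 0.3, and 0.53, 0.61 and 0.79 at r = 0.7. Most of the gain is then at T2.

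**The case against.** The strongest reply is that the SAP has already made a valid choice. Eq. 1 has no condition main effect and the SAP rules out adjustment and subtraction, so the coefficients can only be differences from C1 within each time point. The protocol's comparison with the morning sample can be read as change within each condition, which Eq. 1 does estimate. T1 can be the time reference without being a covariate. All of this stands.

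A reader might infer that the two documents contradict each other, or that the reported effect cannot be identified. The text does not support either. What is missing is an explicit list of contrasts.

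A second reply is that rho may be low. T2 is four hours after T1. T1 is also handled differently: "The remaining samples (morning samples) will be frozen by the participants themselves", at −20°C for up to four days, whereas post-exercise samples go straight to −80°C. This stands too. At rho of 0.2 or less the gain is negligible, and at T4 it may be nil.

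A third reply is that a rich covariance model for each of more than 1,000 metabolites and up to 1,100 lipids would be heavy and prone to singular fits. That is a fair reason to prefer a simple covariate adjustment. It does not justify ignoring T1, because such an adjustment with a time-specific slope cost no more than about 3% in variance, with complete data, in any setting checked.

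**Conclusion.** The point holds as a modest efficiency concern. With complete data, same-day T1 has exactly zero weight in the T2 to T4 condition contrasts. At n = 20, adjustment costs about 3% in variance if rho is 0 and saves about 7% at 0.3, 23% at 0.5 and 48% at 0.7, if rho is constant across T2 to T4. If the correlation decays with clock time, the savings at T3 and T4 are smaller.

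Two stronger readings should be resisted. The first is that Eq. 1 gives biased exercise effects. Order is randomised, so without carry-over or chance period imbalance the plain and adjusted contrasts target the same quantity. The second is that T1 should be subtracted because the protocol calls it a baseline. Subtraction raises the variance whenever rho is below 0.5.

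The conclusion rests on an assumed range for rho, complete data and no carry-over into T1. The priority is optional to moderate.

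**What to change.** In SAP step 3, name the target contrasts: C2 minus C1 and C3 minus C1 at T2, T3 and T4. Replace the rule against using baseline with adjustment for same-day T1. One workable form models T2 to T4 as outcomes, with:

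- time and time:condition;
- the woman's mean T1 over her days;
- the same-day deviation from that mean, with its own slope at each time point;
- (1|id) + (1|id:condition).

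State that T1 will not be subtracted. Keep unadjusted Eq. 1 as a sensitivity analysis. It also covers days with T1 missing and gives change from T1 within a condition. If Eq. 3 is kept for RM-ASCA+, label those effects as unadjusted.

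The cost is SAP wording and a new formula, with no new data. The downsides to state are:

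- About 3% higher variance at n = 20 if rho is near zero.
- Loss of days without T1. If 10% of days lacked it (assumed), a T1-covariate model had multipliers of 1.24, 1.12 and 0.92 at rho 0, 0.3 and 0.5, so missing T1 can outweigh the gain. The protocol's target of 20 women with complete data limits this.
- An assumption that the previous condition does not carry over into T1.
- Possible singular fits for some variables.
- Changed standard errors from the id:condition term, which is a model change in its own right and should be declared as one.
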